7.1.2. Serious Adverse Events

A **serious adverse event** (SAE) is defined as an event that, at any dose, results in the following:

- Death
- Life-threatening (Note: The term "life-threatening" in the definition of "serious" refers to an event in which the subject was at risk of death at the time of the event; it does not refer to an event that hypothetically might have caused death if it were more severe.)
- In-patient hospitalization or prolongation of existing hospitalization
- Persistent or significant disability/incapacity

- A congenital anomaly/birth defect
- A medically important event or reaction: such events may not be immediately life-threatening or result in death or hospitalization but may jeopardize the subject or may require intervention to prevent one of the other outcomes constituting SAEs. Medical and scientific judgment must be exercised to determine whether such an event is a reportable under expedited reporting rules. Examples of medically important events include intensive treatment in an emergency room or at home for allergic bronchospasm; blood dyscrasias or convulsions that do not result in hospitalization; and development of drug dependency or drug abuse. For the avoidance of doubt, infections resulting from contaminated medicinal product will be considered a medically important event and subject to expedited reporting requirements.

7.1.3. Clinical Laboratory Abnormalities and Other Abnormal Assessments as Adverse Events or Serious Adverse Events

Laboratory abnormalities without clinical significance are not recorded as AEs or SAEs. However, laboratory abnormalities (eg, clinical chemistry, hematology, and urinalysis) that require medical or surgical intervention or lead to IMP interruption, modification, or discontinuation must be recorded as an AE, as well as an SAE, if applicable. In addition, laboratory or other abnormal assessments (eg, electrocardiogram, x-rays, vital signs) that are associated with signs and/or symptoms must be recorded as an AE or SAE if they meet the definition of an AE or SAE as described in Sections 7.1.1 and 7.1.2. If the laboratory abnormality is part of a syndrome, record the syndrome or diagnosis (eg, anemia), not the laboratory result (ie, decreased hemoglobin).

For specific information on handling of clinical laboratory abnormalities in this study, please refer to Section 7.5.

7.2. Assessment of Adverse Events and Serious Adverse Events

The investigator or qualified subinvestigator is responsible for assessing AEs and SAEs for causality and severity, and for final review and confirmation of accuracy of event information and assessments.

7.2.1. Assessment of Causality for Study Drugs and Procedures

The investigator or qualified subinvestigator is responsible for assessing the relationship to IMP therapy using clinical judgment and the following considerations:

- No: Evidence exists that the adverse event has an etiology other than the IMP. For SAEs, an alternative causality must be provided (eg, pre-existing condition, underlying disease, intercurrent illness, or concomitant medication).
- Yes: There is reasonable possibility that the event may have been caused by the investigational medicinal product.

It should be emphasized that ineffective treatment should not be considered as causally related in the context of adverse event reporting.

The relationship to study procedures (eg, invasive procedures such as venipuncture or biopsy) should be assessed using the following considerations:

- No: Evidence exists that the adverse event has an etiology other than the study procedure.
- Yes: The adverse event occurred as a result of protocol procedures, (eg., venipuncture)

7.2.2. Assessment of Severity

Severity of adverse events is to be determined based on GSI Grading Scale for Severity of Adverse Events and Laboratory Abnormalities (Appendix 4). A distinction should be drawn between seriousness and severity of AEs. An AE that is assessed as Grade 4 (potentially life-threatening) should not be confused with an SAE. Severity is a category utilized for rating the intensity of an event: both AEs and SAEs can be assessed as Grade 4. An event is defined as "serious" when it meets one of the predefined outcomes described above in Section 7.1.2.

7.3. Investigator Requirements and Instructions for Reporting Adverse Events and Serious Adverse Events to Gilead

Requirements for collection prior to study drug initiation:

After informed consent, but prior to initiation of study medication, the following types of events should be reported on the case report form (CRF/eCRF): all SAEs and adverse events related to protocol-mandated procedures.

Adverse Events

Following initiation of study medication, collect all AEs, regardless of cause or relationship, until 30-days after last administration of study IMP must be reported to the CRF/eCRF database as instructed.

All AEs should be followed up until resolution or until the adverse event is stable, if possible. Gilead Sciences may request that certain AEs be followed beyond the protocol defined follow up period.

Serious Adverse Events

All SAEs, regardless of cause or relationship, that occurs after the subject first consents to participate in the study (ie, signing the informed consent) and throughout the duration of the study, including the protocol-required post treatment follow-up period, must be reported to the CRF/eCRF database and Gilead Drug Safety and Public Health (DSPH) as instructed. This also includes any SAEs resulting from protocol-associated procedures performed after informed consent is signed.

Any SAEs and deaths that occur after the post treatment follow-up visit but within 30-days of the last dose of study IMP, regardless of causality, should also be reported.

Investigators are not obligated to actively seek SAEs after the protocol defined follow up period; however, if the investigator learns of any SAEs that occur after study participation has concluded and the event is deemed relevant to the use of IMP, he/she should promptly document and report the event to Gilead DSPH.

• All AEs and SAEs will be recorded in the CRF/eCRF database within the timelines outlined in the CRF/eCRF completion guideline.

Electronic Serious Adverse Event (eSAE) Reporting Process

- Site personnel record all SAE data in the eCRF database and from there transmit the SAE information to Gilead DSPH within 24 hours of the investigator's knowledge of the event. Detailed instructions can be found in the eCRF completion guidelines.
- If for any reason it is not possible to record the SAE information electronically, ie, the eCRF database is not functioning, record the SAE on the paper serious adverse event reporting form and submit within 24 hours to:

Gilead DSPH:
Fax: PPD
Email: PPD

Medical Monitor:
PPD
Phane: PPD

Phone: PPD
Fax: PPD
Email: PPD

- As soon as it is possible to do so, any SAE reported via paper must be transcribed into the eCRF Database according to instructions in the eCRF completion guidelines.
- If an SAE has been reported via a paper form because the eCRF database has been locked, no further action is necessary.
- For fatal or life-threatening events, copies of hospital case reports, autopsy reports, and other documents are also to be submitted by e-mail or fax when requested and applicable.
 Transmission of such documents should occur without personal subject identification, maintaining the traceability of a document to the subject identifiers.
- Additional information may be requested to ensure the timely completion of accurate safety reports.
- Any medications necessary for treatment of the SAE must be recorded onto the concomitant medication section of the subject's CRF/eCRF and the event description section of the SAE form.

7.4. Gilead Reporting Requirements

Depending on relevant local legislation or regulations, including the applicable US FDA Code of Federal Regulations, the EU Clinical Trials Directive (2001/20/EC) and relevant updates, and other country-specific legislation or regulations, Gilead may be required to expedite to worldwide regulatory agencies reports of SAEs, serious adverse drug reactions (SADRs), or suspected unexpected serious adverse reactions (SUSARs). In accordance with the EU Clinical Trials Directive (2001/20/EC), Gilead or a specified designee will notify worldwide regulatory agencies and the relevant IEC in concerned Member States of applicable SUSARs as outlined in current regulations.

Assessment of expectedness for SAEs will be determined by Gilead using reference safety information specified in the investigator's brochure or relevant local label as applicable.

All investigators will receive a safety letter notifying them of relevant SUSAR reports associated with any study IMP. The investigator should notify the IRB or IEC of SUSAR reports as soon as is practical, where this is required by local regulatory agencies, and in accordance with the local institutional policy.

7.5. Toxicity Management

- All clinical and clinically significant laboratory toxicities will be managed according to uniform guidelines detailed in Appendix 3.
- Grade 3 and 4 clinically significant laboratory abnormalities should be confirmed by repeat testing within 3 calendar days of receipt of results and before investigational medicinal product discontinuation, unless such a delay is not consistent with good medical practice.
- Clinical events and clinically significant laboratory abnormalities will be graded according to the Table for GSI Grading Scale for Severity of Adverse Events and Laboratory Abnormalities (Appendix 4).
- When restarting investigational medicinal product following resolution of the adverse event, the investigational medicinal product should be restarted at full dose or modified dose that is dependent upon discussion with the Gilead Sciences Medical Monitor.
- Any recurrence of the investigational medicinal product-related Grade 3 or 4 clinical or clinically significant laboratory adverse event following dose interruption mandates permanent discontinuation of investigational medicinal product.
- Administration of study drug may be discontinued due to a clinical or laboratory event. The
 Gilead Medical Monitor should be consulted prior to dose discontinuation of study drug
 unless the investigator believes that immediate action is warranted to ensure the continued
 safety of subject.
- Any questions regarding toxicity management should be directed to the Gilead Sciences Medical Monitor.

7.5.1. Grades 1 and 2 Laboratory Abnormality or Clinical Event

• Continue investigational medicinal product at the discretion of the investigator.

7.5.2. Grade 3 Laboratory Abnormality or Clinical Event

- For Grade 3 clinically significant laboratory abnormality or clinical event, investigational medicinal product may be continued if the event is considered to be unrelated to investigational medicinal product.
- For a Grade 3 clinical event, or clinically significant laboratory abnormality confirmed by repeat testing, that is considered to be related to investigational medicinal product, investigational medicinal product should be withheld until the toxicity returns to ≤ Grade 2.
- If a laboratory abnormality recurs to ≥ Grade 3 following rechallenge with investigational medicinal product and is considered related to investigational medicinal product, then investigational medicinal product should be permanently discontinued and the subject managed according to local practice. Recurrence of laboratory abnormalities considered unrelated to investigational medicinal product may not require permanent discontinuation.

7.5.3. Grade 4 Laboratory Abnormality or Clinical Event

- For a Grade 4 clinical event or clinically significant Grade 4 laboratory abnormality confirmed by repeat testing that is considered related to investigational medicinal product, investigational medicinal product should be permanently discontinued and the subject managed according to local practice. The subject should be followed as clinically indicated until the laboratory abnormality returns to baseline or is otherwise explained, whichever occurs first. A clinically significant Grade 4 laboratory abnormality that is not confirmed by repeat testing should be managed according to the algorithm for the new toxicity grade.
- Investigational medicinal product may be continued without dose interruption for a clinically non-significant Grade 4 laboratory abnormality (e.g., Grade 4 CK after strenuous exercise, or triglyceride elevation that is non-fasting or that can be medically managed) or a clinical event considered unrelated to investigational medicinal product.

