7.5.5. On-Treatment ALT Flare and Post-Treatment Exacerbation of Hepatitis Management

On-Treatment ALT Flare is defined as:

• Confirmed (within 3 days of receipt of initial laboratory results) serum ALT > $2 \times$ baseline value and > $10 \times$ ULN, with or without associated symptoms

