7.5.5.1. Management of ALT Flare in Subjects Receiving Study Medication

If laboratory results indicate elevation of ALT $> 2 \times$ baseline and $> 10 \times$ ULN, the following is recommended:

- Schedule the subject to return to the clinic as soon as possible (ideally within 3 days after initial laboratory results were drawn). During the visit, a clinical assessment of the subject will be performed. The assessment should include a physical examination and evaluation of the subject's mental status.
- Check the following laboratory parameters: serum ALT and AST, total bilirubin, INR, and serum albumin.
- If the ALT elevation is confirmed, the central clinical laboratory will conduct reflex testing for plasma HBV DNA, serology for HBV (HBsAg and HBsAb), HDV, HAV IgM, HCV, and HEV.

Based on the results of the confirmatory tests, the following treatment modifications are recommended:

Elevated Liver Enzymes, Normal or Stable relative to baseline Liver Function Tests

If ALT levels are elevated (i.e., $> 2 \times$ baseline and $> 10 \times$ ULN) with normal or stable total bilirubin and INR relative to baseline, the subject may remain on study medication and should be monitored weekly as long as ALT levels return to normal or baseline level.

During monitoring, if the ALT values remain persistently elevated, the investigator should discuss with the Gilead Medical Monitor whether the study drug should be discontinued.

For subjects with bridging fibrosis or cirrhosis, study drug discontinuation with treatment-free follow-up is to be avoided due to the potential risk of exacerbation of hepatitis in the setting of low hepatic reserve which could lead to decompensation. Subjects with bridging fibrosis or cirrhosis should be placed on commercially available HBV therapy following study drug discontinuation.

Elevated Liver Enzymes, Elevated Liver Function Tests

If ALT values are elevated (i.e., $> 2 \times$ baseline and $> 10 \times$ ULN), and total bilirubin is confirmed to be $2 \times$ baseline value, and INR is 0.5 above baseline, provided both are > ULN, the investigator should consider discontinuing study medication (upon discussion with the Gilead Medical Monitor, unless the safety of the subject is of immediate concern).

The subject should be monitored weekly as long as ALT, total bilirubin, and INR values remain elevated or above baseline values.

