Creatinine**	> 1.50 to 2.00 mg/dL	> 2.00 to 3.00 mg/dL	> 3.00 to 6.00 mg/dL	> 6.00 mg/dL	
	$>$ 133 to 177 μ mol/L	> 177 to 265 $\mu mol/L$	> 265 to 530 μmol/L	$> 530 \ \mu mol/L$	
Bicarbonate	16.0 mEq/L to < LLN	11.0 to < 16.0 mEq/L	8.0 to < 11.0 mEq/L	< 8.0 mEq/L	
Adult and Pediatric ≥ 4 Years	16.0 mmol/L to < LLN	11.0 to < 16.0 mmol/L	8.0 to < 11.0 mmol/L	< 8.0 mmol/L	
Pediatric < 4 Years	NA	11.0 mEq/Lto <lln< td="">8.0 to < 11.0 mEq/L	< 8.0 mEq/L	</lln<>	8.0 to < 11.0 mEq/L	< 8.0 mEq/L	
		11.0 mmol/L to <lln< td="">8.0 to < 11.0 mmol/L	< 8.0 mmol/L	</lln<>	8.0 to < 11.0 mmol/L	< 8.0 mmol/L	
Triglycerides	NA	500 to 750 mg/dL	> 750 to 1200 mg/dL	> 1200 mg/dL	
(Fasting)		5.64–8.47 mmol/L	> 8.47–13.55 mmol/L	> 13.55 mmol/L	
LDL (Fasting)	130 to 160 mg/dL	>160 to 190 mg/dL	> 190 mg/dL	NA	
Adult	3.35 to 4.15 mmol/L	>4.15 to 4.92 mmol/L	>4.92 mmol/L		
LDL (Fasting)	110 to 130 mg/dL	>130 to 190 mg/dL	> 190 mg/dL	NA	
Pediatric >2 to <18 years	2.84 to 3.37 mmol/L	>3.37 to 4.92 mmol/L	>4.92 mmol/L		
Hypercholesterolemia	200 to 239 mg/dL	> 239 to 300 mg/dL	> 300 mg/dL	NA	
(Fasting)	5.16 to 6.19 mmol/L	> 6.19 to 7.77 mmol/L	> 7.77 mmol/L		
Pediatric < 18 Years	170 to 199 mg/dL	> 199 to 300 mg/dL	> 300 mg/dL	NA	
	4.39 to 5.15 mmol/L	> 5.15 to 7.77 mmol/L	> 7.77 mmol/L		
Creatine Kinase	$3.0 \text{ to} < 6.0 \times \text{ULN}$	6.0 to < 10.0 × ULN	10.0 to < 20.0 × ULN	≥ 20.0 × ULN	

Calcium should be corrected for albumin if albumin is < 4.0 g/dL

An overlap between the Grade 1 scale and the Lab's normal range for creatinine may result for Male subjects >70 yrs. Please follow the Gilead convention of grading any result within the LLN and ULN a 0.

ENZYMES				
	Grade 1	Grade 2	Grade 3	Grade 4
AST (SGOT)	1.25 to 2.50 × ULN	> 2.50 to 5.00 × ULN	> 5.00 to 10.00 × ULN	> 10.00 × ULN
ALT (SGPT)	1.25 to 2.50 × ULN	> 2.50 to 5.00 × ULN	> 5.00 to 10.00 × ULN	> 10.00 × ULN
GGT	1.25 to 2.50 × ULN	> 2.50 to 5.00 × ULN	> 5.00 to 10.00 × ULN	> 10.00 × ULN
Alkaline Phosphatase	1.25 to 2.50 × ULN	> 2.50 to 5.00 × ULN	> 5.00 to 10.00 × ULN	> 10.00 × ULN
Total Amylase	> 1.0 to 1.5 × ULN	> 1.5 to 2.0 × ULN	> 2.0 to 5.0 × ULN	> 5.0 × ULN
Pancreatic Amylase	> 1.0 to 1.5 × ULN	> 1.5 to 2.0 × ULN	> 2.0 to 5.0 × ULN	> 5.0 × ULN
Lipase	> 1.0 to 1.5 × ULN	> 1.5 to 3.0 × ULN	> 3.0 to 5.0 × ULN	> 5.0 × ULN
Albumin	-	2.0 to < LLN g/dL	< 2.0 g/dL	NA
Pediatrics <16 years		20 to < LLN g/L	< 20 g/L	
	3.0 g/dL to < LLN	2.0 to < 3.0 g/dL	< 2.0 g/dL	NA

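### A confirmed ALT flare judged clinically significant and drug-related is to be stopped permanently under Protocol 7.5.3 but may continue on drug under 7.5.5.1, and the text reviewed does not say which section governs

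*Protocol*

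**What the plan says.** - **Grading.** In the ALT row of Protocol Appendix 4, "> 5.00 to 10.00 × ULN" is Grade 3 and anything higher is Grade 4.
- **Grade 4 rule (Protocol 7.5.3).** For a clinically significant Grade 4 laboratory abnormality the text reads: "confirmed by repeat testing that is considered related to investigational medicinal product, investigational medicinal product should be permanently discontinued". The only laboratory exception is: "Investigational medicinal product may be continued without dose interruption for a clinically non-significant Grade 4 laboratory abnormality". Its examples are creatine kinase after exercise and triglycerides; ALT is not named.
- **Grade 3 rule (Protocol 7.5.2).** If the abnormality is clinically significant, confirmed and related, "investigational medicinal product should be withheld until the toxicity returns to ≤ Grade 2".
- **Flare definition (Protocol 7.5.5).** "Confirmed (within 3 days of receipt of initial laboratory results) serum ALT" above 2 × baseline and above 10 × ULN, with or without symptoms.
- **Flare management (Protocol 7.5.5.1).** "Based on the results of the confirmatory tests, the following treatment modifications are recommended". With normal or stable bilirubin and INR, "the subject may remain on study medication and should be monitored weekly as long as ALT levels return to normal or baseline level". When bilirubin and INR are both raised to the stated extent, the investigator is asked to consider stopping. Where bridging fibrosis or cirrhosis is known, the section adds this caution: "study drug discontinuation with treatment-free follow-up is to be avoided due to the potential risk of exacerbation of hepatitis".
- **General rules (Protocol 7.5).** Toxicities are managed under uniform guidelines in Appendix 3. The Medical Monitor should be consulted before study drug is discontinued, unless immediate action is needed for safety.

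**The concern.** Two sections written for the same laboratory value lead to different actions on whether antiviral treatment continues. ALT flare on treatment and hepatitis exacerbation after stopping are hepatic risks that the protocol itself singles out, and subjects with compensated cirrhosis are eligible (Protocol 3.1). Two sites that both follow the protocol could therefore treat like subjects differently during a hepatic event. The warning about stopping in advanced fibrosis is also missing from 7.5.2 and 7.5.3, the two sections that tell the investigator to hold or stop drug. A secondary consequence is that counts of AE-related discontinuation, including the tolerability-failure summary in the Protocol synopsis, would depend partly on which section was applied.

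**Working it through.** No design calculation is at issue. The check is whether the triggers overlap and whether the actions then differ.

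**1. Do the triggers coincide?** A flare requires ALT > 10 × ULN, and Grade 4 ALT is > 10.00 × ULN, so every flare is Grade 4. The flare definition also requires ALT > 2 × baseline. Protocol 4.3 excludes ALT > 5 × ULN. If ALT is still ≤ 5 × ULN at baseline, then 2 × baseline ≤ 10 × ULN, and any ALT > 10 × ULN also exceeds 2 × baseline. The two triggers are then the same value.

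**2. Do the actions agree?** For a confirmed, clinically significant ALT judged related:

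| ALT | Bilirubin and INR | Protocol 7.5.2 / 7.5.3 | Protocol 7.5.5.1 |
|---|---|---|---|
| > 5 to 10 × ULN | any | withhold to Grade 2 or below | does not apply |
| > 10 × ULN | normal or stable | permanent discontinuation | may continue, with weekly monitoring |
| > 10 × ULN | both raised as specified | permanent discontinuation | consider discontinuing |

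The actions differ in both rows above 10 × ULN. Relatedness, a deciding condition in 7.5.3, plays no part in 7.5.5.1.

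**3. Does giving 7.5.5.1 priority remove the problem?** Not fully. It does not reach the Grade 3 range, so a related ALT of > 5 to 10 × ULN would still be withheld while a higher one could continue.

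**4. Fibrosis or cirrhosis.** The caution is in 7.5.5.1. Sections 7.5.2 and 7.5.3 do not repeat it. Protocol 3.1 strongly encourages alternative HBV therapy after permanent discontinuation, which partly covers 7.5.3. No equivalent wording covers a temporary hold under 7.5.2.

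**5. Size.** Inputs are from Protocol 1.2.3 (Hepatic Flares; Adverse Events by Severity), with 866 TAF and 432 TDF subjects.
- Confirmed flares through Week 48: (5 + 4)/(866 + 432) = 9/1298 = 0.69%; × 460 = 3.2.
- Those studies confirmed a flare at two consecutive visits, whereas this protocol uses a prompt retest. If all ALT elevations had been confirmed: (16 + 9)/1298 = 25/1298 = 1.93%; × 460 = 8.9.
- Grade 3 ALT adverse events judged related: (3 + 1)/1298 = 4/1298; × 460 = 1.4. These were 4 of 8 subjects with such events, so relatedness is a live judgement. No Grade 4 adverse event was recorded.

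The flare figures are not filtered for clinical significance or relatedness. Those studies enrolled viraemic subjects (median HBV DNA 5.7 and 7.9 log10 IU/mL), and this trial enrols suppressed ones, so lower rates would be expected here.

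**The case against.** The strongest reply is that 7.5.5.1 is specific to ALT and a reader would naturally let it govern. It is framed as a recommendation, and continuation under it comes with conditions: stable bilirubin and INR, weekly monitoring, and discussion with the Medical Monitor if ALT stays high. Section 7.5.3 says should, not must, and applies only to clinically significant abnormalities. Medical Monitor consultation before stopping is an added safeguard. Finally, Appendix 3 is cited as the uniform guideline and could contain an ALT exception.

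Most of this is fair and limits the point. What it does not do is supply a rule of precedence. Section 7.5.3 neither exempts ALT nor refers to 7.5.5, and priority for the specific section would leave the Grade 3 inversion. Consultation reduces variation between sites but does not remove it. Appendix 3 is listed in the contents but was not in the text available, so its absence here is not counted as a fault.

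Three stronger readings are tempting and not supported:

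- **Lost BMD and eGFR data.** A reader might infer that a stopped subject contributes no on-treatment values. Earlier visit values remain, and the early-discontinuation visit collects eGFR, plus DXA if none was done in the past 12 weeks (Protocol 6.5). An LOCF analysis is planned for the key secondary safety endpoints (Protocol 8.3). The SAP counts DXA up to 14 days after the last blinded dose as on-treatment and opens its Week 48 BMD window at Day 253 (SAP 3.6.2).
- **Bias in the primary endpoint.** Under Protocol 8.6.1.1, a subject who stops for a reason other than lack of efficacy falls into the no-virologic-data category only if there is no on-treatment HBV DNA in the Week 48 window and the last value is < 20 IU/mL. If that last value is ≥ 20 IU/mL, the subject counts as ≥ 20. Treatment is blinded to Week 48, and nothing shows a difference between arms.
- **Larger counts.** Applying the raw Phase 3 laboratory rates to 460 gives about 11 Grade 4 and 28 Grade 3 ALT results. These are not filtered for confirmation, significance or relatedness, and the Grade 3 results fall outside the conflict between 7.5.3 and 7.5.5.1.

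**Conclusion.** The contradiction holds as a matter of text. For a confirmed ALT flare judged clinically significant and related, 7.5.3 and 7.5.5.1 give different actions, 7.5.2 can be stricter for a lower ALT, and the fibrosis/cirrhosis caution is not carried across. This rests on the Appendix 4 grading and on the available text having no precedence rule; Appendix 3 could narrow it.

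Few subjects would be affected: about 3 confirmed flares per 460 over 48 weeks at the Phase 3 rate, about 9 if every elevation were confirmed on retest, and fewer after filtering for significance and relatedness. The case rests on subject safety and uniform conduct. The analysis effect is limited to a minor one on counts of AE-related discontinuation. No view is taken on which clinical rule is right.

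**What to change.** Reconcile Protocol 7.5.2, 7.5.3 and 7.5.5.1, together with Appendix 3, for ALT:

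- State which section governs ALT elevations in the Grade 3 and Grade 4 ranges, and add cross-references between the sections.
- State whether the fibrosis/cirrhosis caution applies wherever study drug can be held or stopped, including a temporary hold.

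The sponsor's medical team decides which rule stands. The cost is wording in one amendment or a memo to sites. No procedure, sample size or analysis changes.
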